Title: Clinical Investigation Plan. HYROS (HYbrid RObotic Surgery in urology)

Standards and applying chapters: **According to IF-PR01-022 Bitrack_Applicable Regulation and IF-PR01-023_A8 Bitrack Applicable standards**

Protocol Nr: **PL-PR01-027**

[figure not shown]
[figure not shown]
[figure not shown]
[figure not shown]
[figure not shown]
[figure not shown]
[figure not shown]
[figure not shown]
[figure not shown]
[figure not shown]
[figure not shown]
[figure not shown]
[figure not shown]
Revision Nr: **A2**

Date of issue: **04-OCT-2022**

Project Code: **PR01**

Author: **AKRN Scientific Consulting**

REVIEW HISTORY

Reviewed Edition	Date	Section	Rationale	List of Changes
A1	05-Sep-2022	NA	Initial document release	NA
A2	04-Oct-2022	NA	Response to EC comments	Update the version of CIP and date of issue                    
		4		                   
		4.1		                   
		7.1.1		                   
		10.4.1		                   
		13.1		                   

 CONFIDENTIAL
 PL-PR01-027_A2

SUMMARY OF CHANGES

Revision	Summary of Changes
1.0	Document release
2.0	Response to EC comments

CONFIDENTIAL
PL-PR01-027_A2

CONTACT INFORMATION

SPONSOR AND LEGAL MANUFACTURER

Rob Surgical Systems, S.L.

[name]

[REDACTED]

[REDACTED]

Central CRO:

AKRN Scientific Consulting S.L.

[REDACTED]

[REDACTED]

SITE PRINCIPAL INVESTIGATOR:

Hospital Clinic de Barcelona

[REDACTED]

[REDACTED]

[figure not shown]
[figure not shown]
[figure not shown]
[figure not shown]
[figure not shown]
[REDACTED]

CLINICAL INVESTIGATION PLAN (CIP) SUMMARY

Version Number	2.0
Date	04-October-2022
Sponsor	Rob Surgical Systems, S.L. [name]
Clinical Investigation Identification	HYROS
Title	HYbrid RObotic Surgery in urology
Objectives	
The purpose of this early feasibility clinical investigation is to evaluate the safety and feasibility of the Bitrack System and its corresponding ESE and NESE instruments [REDACTED] in patients with the indication of a robot assisted laparoscopic radical/simple nephrectomy.
 
[REDACTED]
 
[REDACTED]

Device Under Investigation	Bitrack System along with its ESE/NESE instruments
Number of Subjects Required for Clinical Investigation	3 subjects shall be included in this early feasibility clinical investigation
Planned Number of Sites	1 investigational site located in Spain
Clinical Investigation Design	This is a single-center, early feasibility, and first in human (FIH) clinical investigation with a single arm, open label and non-randomized design
Primary Endpoints	
The primary safety and performance endpoints of this early feasibility investigation are:
 
 1) Evaluation of the safety of the Bitrack System by measuring the occurrence of Procedure-Related Adverse Events (PRAEs) and Serious Adverse Events (SAEs) during the procedure and through the 30 days post-procedure period of enrolled patients indicated for robot assisted laparoscopic radical/simple nephrectomy. 2) Evaluation of the performance of the investigational devices by means of its ability to access and reach the target zone, perform all relevant surgical tasks and to be withdrawn efficiently without conversion to MIS or open surgery. The performance of the Bitrack System and the ESE/NESE instruments will be analyzed through the conversion rate to conventional laparoscopy/open surgery.

 CONFIDENTIAL
 PL-PR01-027_A2

Secondary Endpoints	
The secondary endpoints planned for this clinical investigation are listed below:
 
 • All AE(s) events during the procedure and through the 30 days post-procedure will also be assessed, and therefore relationship with the investigational device and/or procedure will be examined by the principal investigator and reported to Rob Surgical. 
 ○ Timeframe: Procedure, discharge, 14 days and 30 days follow-up • Individual safety (i.e., absence of unwanted injure of any tissue) and performance (VAS scale 0-10 following the subjective surgeon's opinion, being 0 a non-functional tool and 10 an instrument that works exactly equivalent to the surgeon/s hands) for each instrument surgical function. 
 ○ Timeframe: Procedure • Blood Loss defined as estimated mL of blood loss, transfusion rates and use of hemostasis agents. 
 ○ Timeframe: Procedure • Operative Time Procedure measurement for the different tasks. 
 ○ Timeframe: Procedure • To evaluate post-operative pain in patients through the Cumulative Analgesic Consumption Score (CACS) during the first week (7days) post-procedure. 
 ○ Timeframe: Discharge • To assess the duration of subject's hospitalization as the Length of Stay (LoS) in hospital calculated from day of admission to day of discharge. 
 ○ Timeframe: Discharge • Patient pain assessment via VAS. Patient interview questions. 
 ○ Timeframe: Discharge, 14- and 30-days post-procedure • Post-procedure complication rates, including the measurement of the comprehensive complication index (CCI) on a scale from 0 (no complications) to 100 (death), and the Clavien-Dindo classification, which consists of 7 grades (I, II, IIIa, IIIb, Iva, Ivb and V), the first one indicating any deviation from the normal postoperative course, the highest-grade indicating death. 
 ○ Timeframe: Discharge, 14 and 30 days follow-up
Subject Follow-up	
Subjects will have a 14-days in clinic visit and a 30-days post-procedure remote clinical follow-up visit

Inclusion Criteria	
 1. Adult subjects between 18 and 90 years old

	
 2. Subjects must provide written informed consent prior to any clinical investigation related procedure 3. Subjects who have been scheduled for a laparoscopic radical/simple nephrectomy surgery 4. Ability and willingness to comply with all study requirements to be evaluated for each study visit
Exclusion Criteria	
 1. Pregnant or breastfeeding women at the time of the surgery 2. Inability to adhere to study-related procedures 3. Subject has known allergy to some of the device components (i.e., stainless steel, etc.) 4. Subjects who participate in another trial which may affect the outcome data on this study or the ability to complete the follow up requirements 5. Subjects not suitable to undergo MIS/MIRS, according to medical criteria 6. Subjects with life expectancy inferior to 3 months 7. Subjects with a BMI ≥ 40. 8. Subjects with severe cardiopulmonary or coronary artery disease, bleeding disorders or that have been submitted to multiple prior operations. 9. Subjects with abuses of active substances or with uncontrolled psychiatric disorders. 10. Subjects scheduled for surgeries intended to be in direct contact with the heart, the central circulatory system or the central nervous system 11. Subjects with any contraindication for the use of the Bitrack System and the ESE/NESE instruments, as specified in the Instructions For Use
Electronic Data Capture	
Expected Duration of the Study	         

CONFIDENTIAL
PI -PR01-027 A2

INVESTIGATOR PROTOCOL SIGNATURE PAGE

Investigator Signature

04-Oct-2022

Date (DD-MMM-YYYY)

Investigator Printed Name

[figure not shown]
Investigator

Study Role

Hospital Clínic de Barcelona

Investigational Site Name

SPONSOR SIGNATURE PAGE

CONFIDENTIAL
PL-PR01-027_A2

COMPLIANCE STATEMENT:

This clinical investigation will be conducted in accordance with this Clinical Investigation Plan, the Declaration of Helsinki, ISO 14155:2020 standards, EU Regulation 2017/745 (MDR) and the appropriate local legislation(s). The most stringent requirements, guidelines or regulations must always be followed. The conduct of the clinical investigation will be approved by the appropriate Ethics Committee (EC) of the respective clinical site and as specified by local regulations. Any additional requirement imposed by the EC will be followed.

CONFIDENTIALITY STATEMENT

1. INTRODUCTION

Laparoscopy is defined as a surgical technique that allows surgical procedures to be performed while minimizing trauma to the body. These procedures require a small incision in the body, which permits the introduction of a video-camera system to help the surgeons perform the surgery^{1,2}. [REDACTED]

[REDACTED]

[REDACTED]

Bitrack System is a tele-assisted surgical robot intended to assist in the accurate control of the exclusive Bitrack System-compatible range of ESE/NESE (electrosurgical and non-electrosurgical endoscopic) instruments. The Bitrack System is composed by a console, a robotic unit and an embedded software.

[REDACTED]

[REDACTED]

[REDACTED]

The primary objective of this clinical investigation is to evaluate the safety and performance of the Bitrack System in patients indicated with robotic assisted laparoscopic Radical/simple nephrectomy surgery. [REDACTED]

[REDACTED]

[REDACTED]

This clinical investigation is sponsored by Rob Surgical Systems (Barcelona, Spain) and will be conducted in accordance with this CIP. [REDACTED]

[REDACTED]

1.1. Background

Laparoscopic surgeries have become the gold standard for many surgical procedures as they allow minimally invasive surgery (MIS) to be performed, thus providing a benefit over an open procedure, including, among others, a reduction in post-operative pain, a decrease in the length of hospital stays, a faster return to daily activities and improved cosmesis, which increases patients' quality of life⁴. New surgical tools, such as the development of robotic-assisted surgery (RAS), have been designed to improve the effectiveness of the process, minimizing the ergonomic and visualization deficiencies of laparoscopy while preserving the advantages of minimally invasive surgery³.

During minimally invasive robotic surgery (MIRS) procedures, the robots employed are not considered autonomous, [REDACTED] [REDACTED]

Nevertheless, decades of continued improvement [REDACTED]

[REDACTED] have significantly increased the potential for these robots to assist during minimally invasive surgeries⁶.

[REDACTED]

[REDACTED]

[REDACTED]

[REDACTED]

[REDACTED] One of the main concerns for surgeons is the absence of haptic sensation; however, RAS permits fine and precise movements, as well as the elimination of tremor, which is argued to compensate the aforementioned disadvantage. Besides, the robotic platforms used in RAS offer the possibility to reduce ergonomic issues by providing a comfortable seating or neutral posture position, avoiding forced unnatural movements and delegating the torquing forces to the robotic arms, decreasing the burden on surgeon's muscles in the sensitive areas like the neck, shoulders, and upper back⁷.

Medical application of laparoscopic procedures includes a wide range of surgical processes, among which the most frequent are gastrointestinal complications, bariatric and metabolic surgeries, and gynecological and

urological applications^{3,4}. [REDACTED]

[REDACTED]

[REDACTED]

[REDACTED] The European Association of Urology indicates that robotic and laparoscopic procedures, such as prostatectomy and partial nephrectomy (RNP), are equivalent, [REDACTED]

[REDACTED] [REDACTED] [REDACTED] it has been also determined that the use of RAS may improve the precision of movements and reduce the risk of damage to the cavernous nerves to maintain erectile function by mechanical trauma, traction or thermal energy^{8,9}.

Bitrack System is a surgical robot indicated to be used during urological surgical procedures, general abdominal laparoscopic surgical procedures, and gynecological laparoscopic surgical procedures. This robot is intended to assist in the accurate control of endoscopic instruments and accessories for visualization and endoscopic manipulation. RAS systems and equipment such as Bitrack System are intended for use in invasive surgical procedures, during which patients are potentially most vulnerable to physical harm. [REDACTED]

[REDACTED]

[REDACTED]

[REDACTED]

[REDACTED]

[REDACTED]

1.3. Rationale for Conducting this Clinical Investigation

Traditional laparoscopic surgery has been associated with ergonomic issues due to prolonged operative times, unnatural body postures, and positioning of trocars. Robotic platforms have been introduced as an option to decrease some of these issues. Bitrack System is presented as an open robotic platform designed to improve efficiency with regards to current robotic systems, reducing limitations of conventional laparoscopy and robotic surgery while maintaining its advantages over the open approach. Additionally, enabling fine and precise movements of the surgical instruments results in accurate control of their corresponding endoscopic surgical instruments in case of urologic laparoscopic surgical procedures carried out by means of an abdominopelvic approach.

[REDACTED]

[REDACTED]

[REDACTED]

[REDACTED]

[REDACTED]

[REDACTED]

2. MEDICAL DEVICE OVERVIEW

[REDACTED]

[REDACTED]

[REDACTED]

[REDACTED]

[REDACTED]

2.1. Device Under Investigation

Bitrack System is an Open Robotic Platform designed to universalize high precision surgery and improve the efficiency on current robotics solutions.

Hybrid surgery is a new surgical approach that allows for combining minimally invasive surgery (MIS) and minimally invasive robotic surgery (MIRS) in the same procedure and to move quickly from MIS to MIRS.

[REDACTED]

Finally, in tele-assisted mode, through the console unit, the console user can take control of the system. The system reproduces the user maneuvers (position and orientation) from the console unit manipulators to the instrument end-effectors.

[REDACTED]

[REDACTED]).

[REDACTED]

[REDACTED]

[REDACTED]

[REDACTED]

[REDACTED]

[REDACTED]

[REDACTED]

[REDACTED]

[REDACTED]

Intended purpose: Mechanical cutting and blunt dissection.

1	2	3	4	5	6
1	1	1	1	1	1
2	2	2	2	2	2
3	3	3	3	3	3
4	4	4	4	4	4
5	5	5	5	5	5
6	6	6	6	6	6
7	7	7	7	7	7
8	8	8	8	8	8
9	9	9	9	9	9
10	10	10	10	10	10
11	11	11	11	11	11
12	12	12	12	12	12
13	13	13	13	13	13
14	14	14	14	14	14
15	15	15	15	15	15
16	16	16	16	16	16
17	17	17	17	17	17
18	18	18	18	18	18
19	19	19	19	19	19
20	20	20	20	20	20
21	21	21	21	21	21
22	22	22	22	22	22
23	23	23	23	23	23
24	24	24	24	24	24
25	25	25	25	25	25
26	26	26	26	26	26
27	27	27	27	27	27
28	28	28	28	28	28
29	29	29	29	29	29
30	30	30	30	30	30
31	31	31	31	31	31
32	32	32	32	32	32
33	33	33	33	33	33
34	34	34	34	34	34
35	35	35	35	35	35
36	36	36	36	36	36
37	37	37	37	37	37
38	38	38	38	38	38
39	39	39	39	39	39
40	40	40	40	40	40
41	41	41	41	41	41
42	42	42	42	42	42
43	43	43	43	43	43
44	44	44	44	44	44
45	45	45	45	45	45
46	46	46	46	46	46
47	47	47	47	47	47
48	48	48	48	48	48
49	49	49	49	49	49
50	50	50	50	50	50
51	51	51	51	51	51
52	52	52	52	52	52
53	53	53	53	53	53
54	54	54	54	54	54
55	55	55	55	55	55
56	56	56	56	56	56
57	57	57	57	57	57
58	58	58	58	58	58
59	59	59	59	59	59
60	60	60	60	60	60
61	61	61	61	61	61
62	62	62	62	62	62
63	63	63	63	63	63
64	64	64	64	64	64
65	65	65	65	65	65
66	66	66	66	66	66
67	67	67	67	67	67
68	68	68	68	68	68
69	69	69	69	69	69
70	70	70	70	70	70
71	71	71	71	71	71
72	72	72	72	72	72
73	73	73	73	73	73
74	74	74	74	74	74
75	75	75	75	75	75
76	76	76	76	76	76
77	77	77	77	77	77
78	78	78	78	78	78
79	79	79	79	79	79
80	80	80	80	80	80
81	81	81	81	81	81
82	82	82	82	82	82
83	83	83	83	83	83
84	84	84	84	84	84
85	85	85	85	85	85
86	86	86	86	86	86
87	87	87	87	87	87
88	88	88	88	88	88
89	89	89	89	89	89
90	90	90	90	90	90
91	91	91	91	91	91
92	92	92	92	92	92
93	93	93	93	93	93
94	94	94	94	94	94
95	95	95	95	95	95
96	96	96	96	96	96
97	97	97	97	97	97
98	98	98	98	98	98
99	99	99	99	99	99
100	100	100	100	100	100

CONFIDENTIAL
PL-PR01-027 A2

2.2. Intended purpose

Bitrack System is intended to assist in the accurate control of endoscopic instruments and accessories for visualization and endoscopic manipulation of tissue including grasping, mechanical and monopolar cutting, dissection and blunt dissection, approximation, ligation, bipolar coagulation, suturing, and delivery, placement and tracking of endoscopic assistance instruments and/or manual instruments. Bitrack System is indicated for use during urological surgical procedures, general laparoscopic surgical procedures, and gynecological laparoscopic surgical procedures. The patient target population of Bitrack System is adults. The intended users are trained physicians in an operating room environment in accordance with the Instructions for Use.

2.3. Intended Indication for Use

Bitract System is a robotic surgical system indicated for urologic, general laparoscopic and gynecologic laparoscopic surgical procedures. The recommended procedures are listed as follows:

- Urology
 - Partial/radical nephrectomy
 - [REDACTED]
 - [REDACTED]
 - Radical prostatectomy
 - [REDACTED]
 - Lysis of Adhesions
 - Lymphadenectomy
 - [REDACTED]

CONFIDENTIAL
PL-PR01-027 A2

Page 1 of 1

CONFIDENTIAL
PL-PR01-027_A2

The image consists of a grid of horizontal bars. The bars are primarily black, set against a white background. On the far left, there are small black dots and a few short horizontal bars. The bars are of varying lengths, with some being significantly longer than others. This pattern of longer and shorter bars is repeated across the entire width of the image. The overall effect is a rhythmic, horizontal pattern of black and white.

CONFIDENTIAL
PL-PR01-027 A2

www.english-test.net

© 2019 Pearson Education, Inc.

111

© 2019 Pearson Education, Inc.

For more information, contact the Office of the Vice President for Research and Economic Development at [contact] or [contact].

Black box

For more information, contact the Office of the Vice President for Research and Economic Development at [contact] or [contact].

2.5. Description of the Control Device(s) or Historic Control

No Control Devices or Historic Control are applicable to this study, since there is no direct comparison to other competitor devices.

2.6. Device Handling

© 2019 Pearson Education, Inc.

Digitized by [contact]

For more information, contact the Office of the Vice President for Research and Economic Development at [contact] or [contact].

ESE/NESE instruments will be handled according to the approved Instructions For Use. Prior to use of the device, there is a non-sterile manipulation of the devices to remove them from third and secondary packaging.

© 2019 Pearson Education, Inc.

■ [About](#) | [Contact](#) | [Feedback](#) | [Help](#) | [Privacy](#) | [Terms](#) | [Sitemap](#) | [Log In](#) | [Sign Up](#)

CONFIDENTIAL
PI -PR01-027 A2

3. CLINICAL INVESTIGATION OBJECTIVE

The purpose of this early feasibility clinical investigation is to evaluate the safety and performance of the Bitrack System and its corresponding ESE and NESE instruments and accessories in patients with the indication of a robot assisted laparoscopic radical/simple nephrectomy.

[REDACTED]

CONFIDENTIAL
PL-PR01-027_A2

4. CLINICAL INVESTIGATION DESIGN

The study will be conducted as an early feasibility clinical investigation with a single arm, open-label, and non-randomized design, and will include 3 subjects candidate to a standard of care laparoscopic surgery.

[figure not shown]
The clinical investigation will be conducted in 1 center in Spain. Therefore, this clinical investigation will be considered as monocentric. The site investigation details are provided below:

Hospital Clinic de Barcelona

The objective of the study is to make a preliminary and exploratory evaluation of the safety and performance of the Bitrack System device and its laparoscopic instruments for the first time in humans, 

 Since the study does not include a formal hypothesis and it is an Early Feasibility Study (EFS) as described by Annex I of EN ISO 14155:2020 on Clinical research with medical devices, the statistical analysis of the sample population is not considered applicable.

4.1. Clinical Investigation Procedures and Follow-up Schedule

The Clinical Investigation visits will occur as in-clinic visits at Baseline, Procedure, Discharge, 14 and 30-days follow-up.

The Flow Chart and the Follow-up phases of this clinical investigation are described in Figure 4-1 below.

[figure not shown]

Figure 4-1. Flowchart of the clinical investigation schedule

The scheduling of the clinical investigation visits will include the following:

Baseline visit (Visit 1)

During the baseline visit, the patient will be informed about the clinical study and provide signed informed consent form if surgeon decides that the patient is eligible as applicable. [REDACTED]
[REDACTED]
[REDACTED]
[REDACTED]

[REDACTED] In case of pregnancy, the patient will withdraw of the study a [REDACTED]
[REDACTED].

Procedure – (Visit 2)

The study population consists of subjects that provided signed ICF, met all inclusion criteria and none of the exclusion criteria, and successfully undergo surgery with the Bitrack System and its corresponding ESE/NESE instruments. These patients will be followed up until 30 days post-procedure. On the other hand, those subjects

in whom robot assisted laparoscopic radical/simple nephrectomy is attempted but not achieved will be followed-up for 30 days, but not included as population for analysis.

For research purposes, we will consider the start of the procedure at the moment of docking, meaning the moment when the camera of the robot is introduced inside the trocar. Therefore, all procedures that started but do not proceed with the use of the Bitrack system or are converted into a conventional laparoscopic/open surgery are included under the Intent-to-treat (ITT) population. Any robot assisted surgery converted to conventional laparoscopic/open surgery due to reasons different than the failure of the Bitrack System and its corresponding sterile endoscopic surgical instruments will be excluded from the endpoint analysis. █

This event will be considered a procedure failure.

CONFIDENTIAL
PI-PR01-027 A2

The diagram consists of six horizontal bars, each ending in a black square. The bars are arranged in two columns of three. The first bar in the first column is shorter than the second. The second bar in the first column is longer than the first. The third bar in the first column is shorter than the second. The fourth bar in the second column is longer than the first. The fifth bar in the second column is shorter than the fourth. The sixth bar in the second column is longer than the fifth.

A horizontal bar consisting of seven thin black lines of varying lengths, with the rightmost line being the longest and blacked out.

Discharge (Visit 3)

Subject's discharge will be completed following site's standard of care practices and always when it is safe for the subject. At the time of discharge, subject's clinical information will be collected to assess the post-operative pain, together with the rate of post-procedure complications.

14-Days follow-up visit (Visit 4)

The objective of this visit is to collect data on AEs related to the device and the procedure.

30-Days follow-up visit (Visit 5)

The objective of this follow-up visit will be to collect data about any AE related to the device, the procedure or both. Additionally, information about the patient pain evaluation will also be gathered.

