5. ENDPOINTS

5.1. Primary Endpoint

The primary safety and performance endpoints of this early feasibility investigation are:

1. Evaluation of the safety of the Bitrack System by measuring the occurrence of Procedure-Related Adverse Events (PRAEs) and Serious Adverse Events (SAEs) during the procedure and through the 30 days post-procedure period of enrolled patients indicated for robot assisted laparoscopic radical/simple nephrectomy.
2. Evaluation of the performance of the investigational devices by means of its ability to access and reach the target zone, perform all relevant surgical tasks and to be withdrawn efficiently without conversion to MIS or open surgery. The performance of the Bitrack System and the ESE/NESE instruments will be analyzed through the conversion rate to conventional laparoscopy/open surgery.

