6.1.1. Number of Subjects

A total of 3 subjects will be enrolled in the clinical investigation.

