6.4. Subject Enrollment

For the HYROS study, a patient is considered enrolled in the clinical investigation from the moment they provide written informed consent, has been confirmed to meet all inclusion criteria and none of the exclusion criteria and has been successfully treated with the Bitrack System.

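### Sections 4.1 and 6.4 remove every converted case from the analysed population, so the primary conversion rate can only be 0% or undefined, and the next paragraph of 4.1 contradicts this

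*Protocol*

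**What the plan says.** Protocol 5.1 makes conversion the measure of primary endpoint 2: performance "will be analyzed through the conversion rate to conventional laparoscopy/open surgery". The visible text then gives several accounts of who is counted.

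- **4.1, Procedure (Visit 2), first paragraph.** The study population is limited to consenting, eligible subjects who "successfully undergo surgery with the Bitrack System and its corresponding ESE/NESE instruments". A subject in whom the robotic nephrectomy "is attempted but not achieved will be followed-up for 30 days, but not included as population for analysis".
- **6.4.** Enrolment requires consent, eligibility and that the patient "has been successfully treated with the Bitrack System".
- **4.1, next paragraph.** The procedure starts at docking. Started procedures that "are converted into a conventional laparoscopic/open surgery are included under the Intent-to-treat (ITT) population". Conversions "due to reasons different than the failure of the Bitrack System and its corresponding sterile endoscopic surgical instruments will be excluded" from the endpoint analysis, which implies that device-failure conversions stay in.
- **9.1.1.** Read literally, the ITT population consists only of patients in whom treatment was tried and not completed.
- **Number of subjects.** Section 4 says the study "will include 3 subjects candidate to a standard of care laparoscopic surgery", while 6.1.1 says "A total of 3 subjects will be enrolled in the clinical investigation".

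Section 9.2.1 restates the primary endpoints without naming the population for the conversion rate.

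**The concern.** A conversion caused by the device is the event that primary endpoint 2 exists to reveal. Under the first paragraph of 4.1 and under 6.4 that event can never appear in the rate. Section 9.3 says the study informs the decision to fix the device design and move on to validation. A 0% that holds by definition would misinform that decision.

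The design is descriptive, so no test, error rate or power is affected. What is affected is whether the primary performance result can carry any information.

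Two related questions follow:

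- If only successes count as enrolled and 3 are to be enrolled, it is unclear whether a converted patient uses one of the three places.
- Primary endpoint 1 is measured in enrolled patients (5.1, 9.2.1), so with 6.4 a converted patient's adverse events could fall outside it. This is only a possible reading: 4.1 keeps the 30-day follow-up, 8.3.2 plans intra-operative event rates, and part of 8.3.1 is redacted.

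**Working it through.** **Inputs.** Three subjects (6.1.1) and the conversion rate as endpoint (5.1). The protocol gives no expected conversion rate and no sample-size calculation (9.3), so there is no planned figure to reproduce. The counts below are illustrations.

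**Notation.** Three procedures are attempted. Let d be the number of device-failure conversions and o the number of conversions for other reasons.

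- Rule A (4.1 first paragraph, 6.4): no conversion is counted, so the rate is 0/(3 − d − o).
- Rule B (4.1 next paragraph): other-cause conversions are dropped and device-failure conversions kept, so the rate is d/(3 − o).
- 9.1.1 read literally: the set holds only failures, so the rate is (d + o)/(d + o).
- All started procedures: (d + o)/3.

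| d | o | Rule A | Rule B | 9.1.1 literal | All started |
|---|---|---|---|---|---|
| 0 | 0 | 0/3 = 0% | 0/3 = 0% | 0/0 undefined | 0/3 = 0% |
| 1 | 0 | 0/2 = 0% | 1/3 = 33% | 1/1 = 100% | 1/3 = 33% |
| 2 | 0 | 0/1 = 0% | 2/3 = 67% | 2/2 = 100% | 2/3 = 67% |
| 3 | 0 | 0/0 undefined | 3/3 = 100% | 3/3 = 100% | 3/3 = 100% |
| 1 | 1 | 0/1 = 0% | 1/2 = 50% | 2/2 = 100% | 2/3 = 67% |
| 0 | 1 | 0/2 = 0% | 0/2 = 0% | 1/1 = 100% | 1/3 = 33% |

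Rule A gives 0% or an undefined rate in every row. Rules A and B part only when at least one conversion is due to device failure. The last row shows that rule B also hides a conversion when the cause is judged to be something else.

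**If 6.4 means recruiting until 3 successes are enrolled** (an assumption; no visible text states a replacement rule), with o = 0 the rate among enrolled is 0/3 and the rate among attempts is d/(3 + d). For d = 1 this is 1/4 = 25%; for d = 2 it is 2/5 = 40%.

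**How likely the conflict is to matter.** The chance of at least one conversion in three attempts is 1 − (1 − p)³. For assumed risks p of 5%, 10%, 20% and 30% (none from the protocol) it is 14.3%, 27.1%, 48.8% and 65.7%. These are risks of any conversion. The chance that rules A and B differ follows the same formula with p as the risk of a device-failure conversion.

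**The case against.** The strongest reply is that the second paragraph of 4.1 is the more specific text and should govern. It defines the start of the procedure, assigns conversions to ITT, and excludes only those not due to the device; that exclusion has no purpose unless device-failure conversions count. On this view the first paragraph merely describes the completed cases, and the defect is poor labelling. In addition:

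- A redaction sits just before the closing sentence of that paragraph, which labels some event a procedural failure, and the hidden text may settle the matter.
- Section 6.4 cannot work literally, since 6.2.1 collects subject data after enrolment and safety is measured during the procedure.
- With three patients at one site, and device deficiencies due to the sponsor within 24 hours (8.3.4), the sponsor would learn of any device-caused conversion anyway.

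Part of this stands. It is not known which rule the sponsor would apply, the redaction hides one referent, and the counts are hypothetical. None of it removes the contradiction. The visible sentence in 4.1 takes uncompleted cases out of the analysis without qualification, and 6.4 points the same way. Reading a conversion as an uncompleted case is natural, because 5.1 itself describes good performance as finishing without conversion. Deficiency reporting informs the sponsor but does not repair the endpoint. Nor can this be left to an analysis plan: the protocol itself fixes the population in conflicting ways, so an analysis plan could follow one passage only by breaching another.

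**Conclusion.** The concern holds, and the text must be corrected before the primary performance endpoint can be interpreted. If the first paragraph of 4.1 and section 6.4 are followed, the conversion rate is 0% whenever any case is completed and undefined otherwise. If the next paragraph of 4.1 is followed, one device-failure conversion in three attempts gives 33%. If 9.1.1 is taken literally as the denominator, any conversion forces 100%. At this sample size one reclassified patient moves the result from 0% to 33%.

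This rests on two assumptions: that a converted case is one in which the robotic procedure was not completed, and that the redacted words in 4.1 do not cancel the visible ones. The numerical contrasts further assume three attempts, without replacement except where stated.

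**What to change.** Amend the wording as follows.

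- **4.1:** delete the clause that takes uncompleted cases out of the analysis, and the restriction of the study population to successful surgery.
- **6.4 and 6.1.1:** remove successful treatment from the enrolment definition, and state whether the 3 subjects are started or completed procedures.
- **9.1.1:** define ITT as every patient in whom the Bitrack procedure was started, using the docking definition already in 4.1, whether completed or not.
- **Primary endpoints:** use that set for both, and align the reference to enrolled patients in the CIP summary, 5.1 and 9.2.1. Because docking comes after the trocar is in place, also state where safety events in a patient who never reaches docking are reported.
- **Reporting:** give the number of conversions out of all started procedures with the cause of each, so that both the device-failure and the all-cause rate can be read. Whether other-cause conversions are left out of the headline rate is the sponsor's choice, provided they are still shown.

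Check the new text against the redacted parts of 4.1 and 8.3.1.

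The cost is a protocol amendment with ethics committee and AEMPS review. No new data are needed, because 4.1 already follows these patients for 30 days. The reported conversion rate may look less favourable, and the enrolment change can alter which patients count toward the 3.
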